Aim 2: Experimental Study—Probe the acute effects of a sleep phase-stabilizing manipulation on sleep and circadian rhythms, as well as neurobehavioral markers of SUD risk. Compared to the control group, the manipulation group will exhibit: (H2a) advances in circadian phase, increases in sleep duration, and reductions in circadian misalignment; and (H2b) reductions in behavioral and neural (fMRI) measures of increased impulsivity and reward sensitivity.

Exploratory Longitudinal Aim: Examine the prospective relationships between DSP characteristics and changes in SU via repeated bi-monthly assessments during a high-risk period for SU initiation/escalation.

Study Design & Methods

The proposed study will, for the first time, (1) comprehensively characterize the SUD risk profile associated with adolescent DSP, and (2) probe whether SUD risk is diminished by altering sleep/circadian timing. The study will assess both established markers of SUD risk and putative neurobehavioral mechanisms (impulsivity and reward sensitivity). Specifically, we propose a comprehensive, multi-method approach to examining DSP's role in SUD risk, combining laboratory, experimental, and longitudinal studies.

We will recruit a sample of 150 eleventh and twelfth graders (16-19 y/o), divided between 100 DSP and 50 normal phase teens. We will focus on cannabis and alcohol use given their prevalent use in adolescents and evident links to DSP. This study combines Laboratory, Experimental, and Longitudinal protocols.

The Laboratory protocol (aka T1 or Baseline phase) compares a group of DSP adolescents to a group of normal phase adolescents on behavioral and neuroimaging (fMRI) tasks tapping impulsivity and reward sensitivity, as well as a circadian phase assessment. This protocol lasts 1 week, with a weeknight overnight visit at the end.

In the Experimental protocol (aka T2 or Post-Manipulation phase), we will probe whether stabilizing circadian phase in the DSP group by using sleep scheduling and chronotherapeutic approaches (e.g., bright light)

improves sleep and neurobehavioral function relevant to SUD risk. This protocol last 2 weeks, with a weeknight overnight visit at the end.

Finally, in the Longitudinal protocol we include repeated follow-up assessments (bi-monthly for the first 6 months; every 6 months afterwards) of sleep and SU to explore longitudinal associations during the high-risk transition to young adulthood.

Eligibility Criteria

General inclusion criteria:

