- Conditions that would interfere with the MRI procedures. These include the presence of implanted medical devices such as cardiac pacemaker, aneurysm clip, ear implant, IUD, shrapnel, neurostimulators or other metal devices (e.g. dental braces); and fear of closed spaces.

Statistical Considerations

We will calculate actigraphy and EMA summary measures, examine SU distributions, and perform preliminary analyses. For *a priori* hypotheses, all models will be adjusted for potential confounding factors (e.g., sex). P-values and effect sizes with 95% confidence intervals will be used to evaluate statistical and clinical significance, respectively. After model-fitting, diagnostics will be used to evaluate model assumptions and fit. Transformations or non-parametric methods will be used if normality assumptions are violated. Analyses for the experimental study will adhere to an intent-to-treat principle and include all randomized subjects as assigned.

Aim1:

The DSP group will exhibit (H1a) later circadian phase, shorter sleep duration, and greater circadian misalignment and (H1b) greater behavioral and neural evidence of impulsivity and reward sensitivity: We will use a regression model to test the effect of group on each *a priori* outcome, controlling for relevant confounders. H1c: The DSP group will exhibit greater odds of cannabis and alcohol use. We will use a generalized linear model to test whether the relative risk of cannabis use and/or alcohol use in the past month differs by group, controlling for relevant confounders.

Aim 2:

The manipulation group will exhibit (H2a) advances in circadian phase, increases in sleep duration, and reductions in circadian misalignment; and (H2b) reductions in behavioral and neural (fMRI) measures of increased impulsivity and reward sensitivity. Mixed effect models will be used to test the effect of group on changes in each *a priori* outcome, controlling for relevant confounders.

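### Aim 1 (H1a, H1b) compares 100 with 50 teens by adjusted regression with no standard-error type named; HC3 would protect p-values and intervals against unequal group variances at little cost.

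*Combined protocol and SAP*

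**What the plan says.** Study Design & Methods sets the sample at 150, "divided between 100 DSP and 50 normal phase teens". In Statistical Considerations, the Aim 1 paragraph covers all H1a outcomes (circadian phase, sleep duration, misalignment) and all H1b outcomes (behavioral and neural impulsivity and reward sensitivity) with one sentence: "We will use a regression model to test the effect of group on each" a priori outcome, with adjustment for confounders. No standard-error or variance estimator is named.

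The opening paragraph of the same section adds three relevant statements:

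- On inference: "P-values and effect sizes with 95% confidence intervals will be used to evaluate statistical and clinical significance, respectively".
- On checking: "After model-fitting, diagnostics will be used to evaluate model assumptions and fit".
- On remedies: "Transformations or non-parametric methods will be used if normality assumptions are violated".

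Nothing says what is done if the two groups have unequal variances. H1c (generalized linear model) and Aim 2 (mixed models) have their own methods and are outside this point.

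**The concern.** The ordinary regression standard error pools the residual variance over both groups, so the larger group dominates it. When group sizes are equal, the pooling error cancels for the group contrast. At 100 against 50 it does not. If the 50 normal phase teens are the more variable, the standard error is too small, p-values are too low and intervals too narrow. If the 100 DSP teens are the more variable, the test is conservative and loses power.

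The groups are formed by sleep timing and not by randomization, so equal variances are not guaranteed by design. They would have to hold separately for each of many different outcomes. The plan rests both statistical and clinical significance on the p-values and 95% intervals, and both depend on the standard error. Diagnostics might reveal the problem, but no action follows from them.

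**Working it through.** **Inputs from the documents.** Group sizes 100 and 50; regression on group with covariates, sex being the only one named; 95% intervals. The plan states no alpha, SD, effect size or power, so there is no figure of its own to reproduce.

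**Assumptions.** Two-sided 5% test (inferred from the 95% intervals), ordinary standard errors as the default, and SD ratios from 1 to 2 in either direction.

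**Step 1: formula, no covariate.** With SDs s1 (DSP) and s0 (normal phase):

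- Pooled SE = √[((99·s1² + 49·s0²)/148) × (1/100 + 1/50)]
- True SE = √(s1²/100 + s0²/50)
- Actual type I error ≈ 2 × [1 − Φ(1.96 × pooled SE / true SE)]

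Example with s1 = 1, s0 = 1.5: pooled variance = (99 + 110.25)/148 = 1.414; pooled SE = √(1.414 × 0.03) = 0.206; true SE = √(0.01 + 0.045) = 0.235; ratio 0.878; type I error 8.5%.

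Reversed, s1 = 1.5, s0 = 1: pooled variance = (222.75 + 49)/148 = 1.836; pooled SE = √(1.836 × 0.03) = 0.235; true SE = √(0.0225 + 0.02) = 0.206; ratio 1.138; type I error 2.6%.

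**Step 2: simulation of the adjusted model.** Outcome = 0.5 × sex + normal error, sex 50% in both groups, no group effect; regression on group and sex; t reference with 147 df; 40,000 runs per scenario (simulation error about √(0.05 × 0.95/40,000) = 0.1 percentage points).

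| SD ratio | More variable group | Pooled/true SE | Type I error, formula | Type I error, simulated |
|---|---|---|---|---|
| 1 | neither | 1.000 | 5.0% | 5.0% |
| 1.1 | normal phase | 0.969 | 5.8% | 5.7% |
| 1.25 | normal phase | 0.929 | 6.9% | 6.8% |
| 1.5 | normal phase | 0.878 | 8.5% | 8.4% |
| 2 | normal phase | 0.815 | 11.0% | 11.1% |
| 1.1 | DSP | 1.032 | 4.3% | 4.3% |
| 1.25 | DSP | 1.077 | 3.5% | 3.4% |
| 1.5 | DSP | 1.138 | 2.6% | 2.7% |
| 2 | DSP | 1.226 | 1.6% | 1.7% |

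Over the same scenarios HC3 gives type I error of 4.6% to 5.0%. Coverage of the 95% interval runs from 88.9% to 98.3% with ordinary errors and from 95.0% to 95.4% with HC3.

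**Step 3: is the split the cause?** At 75 against 75 with SD ratios of 1 to 2, ordinary type I error is 4.9% to 5.2%. It is.

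**Step 4: robustness.** Adding a continuous covariate gives the same picture: ordinary 1.8% to 10.9%, HC3 4.5% to 5.1%. With 80 and 40 analysed, and normal phase/DSP SD ratios of 0.67, 1 and 1.5, ordinary errors give 2.8%, 5.1% and 8.6%; HC3 gives 4.7%, 4.7% and 5.0%.

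**Step 5: power** (20,000 runs; difference in units of the less variable group's SD).

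| Scenario | Difference | HC3 | Ordinary | Ordinary type I error |
|---|---|---|---|---|
| Equal SDs | 0.50 | 80.9% | 81.5% | 5.0% |
| DSP SD 1.25 times larger | 0.55 | 81.4% | 77.7% | 3.4% |
| DSP SD 1.5 times larger | 0.65 | 86.9% | 80.8% | 2.7% |
| Normal phase SD 1.25 times larger | 0.55 | 75.8% | 80.6% | 6.8% |
| Normal phase SD 1.5 times larger | 0.65 | 77.1% | 84.3% | 8.4% |

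In the last two rows the ordinary test's higher power comes with an inflated error rate.

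**The case against.** **Nothing is shown to be wrong.** The effect needs ordinary standard errors and unequal variances, and the documents establish neither. This stands, and it is why the point is optional. The 11.1% figure needs the normal phase SD to be double. If the bedtime cut alone caused the difference, a normal model with assumed correlations of 0.5 to 0.8 and cuts at the 30th to 70th percentile gives SD ratios of only about 0.89 to 1.13. Retaining teens with insomnia or delayed sleep phase disorder (Eligibility Criteria) could make the DSP group the more variable one, which is the conservative direction.

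**Diagnostics already cover equal variance.** Partly. A median-centred Levene test on the residuals detects SD ratios of 1.1, 1.25, 1.5 and 2 in about 10%, 36% to 37%, 84% and 99.9% of runs. If detection triggered HC3, type I error would be 4.1% to 5.8%, so most of the distortion would go. But the plan states no such rule. Its non-normality remedy would seldom be triggered: a Shapiro-Wilk test on residuals rejected in about 6% of runs at ratio 1.25 and 10% to 15% at 1.5. Nor would a rank test cure it. Unadjusted, Mann-Whitney rejected in 6.9% and 8.6% of null runs at normal phase ratios of 1.5 and 2.

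**HC3 is not exact under skewness.** True. With strongly skewed (lognormal, log-SD 0.8) errors and normal phase ratios of 1.25, 1.5 and 2, HC3 gave 5.5%, 6.1% and 6.6%. Ordinary errors gave 6.6%, 8.2% and 10.9%, so HC3 remains the better choice.

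**Neural outcomes may be maps.** The documents do not say. This limits the proposed sentence to outcomes with one summary value per participant.

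**Conclusion.** The point holds as a cheap, optional improvement and not as a demonstrated error. Under the assumed SD ratios of 1.1 to 2, ordinary standard errors at 100 against 50 give type I error of 5.7% to 11.1% if the normal phase group is the more variable, and 4.3% down to 1.7% if the DSP group is. HC3 stays close to 5% in both directions under normal errors. At equal variances the plan has no problem. Which case applies cannot be told from the documents, and that uncertainty is the reason to choose a standard error that does not depend on the answer. HC3 does nothing about confounding, the choice of covariates or multiplicity.

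**What to change.** Add to the Aim 1 paragraph:

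> For continuous H1a and H1b outcomes analysed as one summary value per participant, the covariate-adjusted regression will use heteroscedasticity-consistent (HC3) standard errors and 95% confidence intervals.

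Keep the existing provision for transformations or non-parametric methods. If any neural outcome is analysed as a map, state its variance handling separately. Naming HC3 in advance also avoids choosing the test after a pre-test on the same data.

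The cost is one sentence. At equal variances intervals are about 1.5% wider (0.701 against 0.691 SD) in the model with an added continuous covariate. In that model the power loss is about 0.5 to 1.2 percentage points for differences of 0.3 to 0.6 SD. No study procedure changes.

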Study Protocol

Official Title: Delayed sleep phase and risk for adolescent substance use

ClinicalTrials.gov ID (NCT number): NCT03806296

Protocol Date: 08.04.2025

Scientific Background

The acceleration of substance use (SU) that often begins in adolescence can culminate in substance use disorders (SUDs) and a host of other poor outcomes. Mounting evidence indicates that sleep and circadian rhythm disturbances are key contributors to adolescent SU. Delayed sleep phase (DSP), a phenotype characterized by later sleep timing, appears to confer particular risk for elevated SU, and ultimately, SUDs. However, the exact nature of this link and the mechanisms underlying it remain unclear. The extant literature is limited both conceptually (e.g., insufficient attention to neurobehavioral mechanisms) and methodologically (e.g., cross-sectional designs and self-report measures). Circadian misalignment resulting from a mismatch between late sleep timing and early school start times is a compelling potential contributor to elevated SU in adolescent DSP with plausible neurobehavioral mechanisms. We hypothesize that DSP-associated circadian misalignment decreases impulse control and increases reward sensitivity, thereby increasing SUD risk.

NOTE: in the ClinicalTrials.gov protocol, the “Delayed Sleep Phase (DSP)” group is referred to as Late Sleep group, and the “normal phase group” is referred to as the Early/Mid Sleep group

Study Objectives

The proposed study will, for the first time, (1) comprehensively characterize the substance use disorder (SUD) risk profile associated with adolescent delayed sleep phase, and (2) probe whether SUD risk is diminished by altering sleep/circadian timing.

Aim 1: Laboratory Study—Compare DSP group to normal phase group on sleep/circadian factors, neurobehavioral markers, and SU. Compared to the normal phase group, the DSP group will exhibit: (H1a) later circadian phase, shorter sleep duration, and greater circadian misalignment; (H1b) greater behavioral and neural evidence of impulsivity and reward sensitivity; and (H1c) greater odds of cannabis and alcohol use.

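### Does H1c need rewording because it predicts higher odds of using cannabis and alcohol, while its test is on the relative risk of using one and/or the other?

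*Combined protocol and SAP*

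**What the plan says.** The hypothesis appears twice in the combined protocol and SAP. Study Objectives, Aim 1, predicts "greater odds of cannabis and alcohol use" in the DSP group. Statistical Considerations, Aim 1, repeats it: "H1c: The DSP group will exhibit greater odds of cannabis and alcohol use". The next sentence there gives the analysis: a generalized linear model, adjusted for confounders, to "test whether the relative risk of cannabis use and/or alcohol use in the past month differs by group".

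Three other places bear on the reading:

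- Study Objectives introduces Aim 1 with "Compare DSP group to normal phase group on sleep/circadian factors, neurobehavioral markers, and SU".
- Study Design & Methods names cannabis and alcohol as the substances of interest and plans 100 DSP and 50 normal phase participants.
- The opening of Statistical Considerations says "P-values and effect sizes with 95% confidence intervals will be used to evaluate statistical and clinical significance, respectively".

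For H1c the document gives no link function, significance level, expected use rates, clinical threshold, or rule for combining the two substances into one verdict.

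**The concern.** Two neighbouring sentences that should describe the same comparison differ in two ways.

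1. **Effect measure.** The hypothesis speaks of odds and the test of relative risk. Above 1, the odds ratio is always further from 1 than the relative risk, and the plan judges clinical significance from effect sizes.
2. **Outcome.** The hypothesis joins the substances with *and*, the test with *and/or*. The test could be two separate yes/no outcomes, one any-use composite, one co-use outcome, or a mix.

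The second difference looks more serious. If only one substance truly differs between groups, a composite or a one-is-enough rule could be reported as support for a hypothesis that names both. If the outcome were chosen after the data had been seen, the choice could shape the conclusion.

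**Working it through.** The plan states no figure for H1c, so there is nothing to reproduce. The check compares the wording and then illustrates each difference. Group sizes (100 and 50) come from Study Design & Methods. Use rates, effect sizes, the correlation between substances and a two-sided 0.05 level are assumptions. Nothing below includes the planned confounder adjustment.

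**Step 1: odds against relative risk.** Let p0 and p1 be the proportions using in the normal phase and DSP groups. Then RR = p1/p0 and OR = [p1/(1−p1)]/[p0/(1−p0)]. Because p/(1−p) rises with p, OR > 1 exactly when p1 > p0, that is, when RR > 1. Direction and null hypothesis are the same; only the number reported differs. For RR = 2:

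| p0 | p1 | OR |
|---|---|---|
| 0.10 | 0.20 | 0.250/0.111 = 2.25 |
| 0.20 | 0.40 | 0.667/0.250 = 2.67 |
| 0.30 | 0.60 | 1.500/0.429 = 3.50 |

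The analysis sentence names relative risk, so the reported number is settled. An analyst choosing a link would take one that yields a relative risk.

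**Step 2: what each outcome would estimate.** Assume normal-phase use of 20% (cannabis) and 30% (alcohol), and OR = 2 for each. With p1 = OR·p0/(1−p0+OR·p0), DSP use is 0.40/1.20 = 0.333 and 0.60/1.30 = 0.462. If use of the two is independent within group:

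| Outcome | Normal phase | DSP | RR | Power, 50 vs 100 |
|---|---|---|---|---|
| Cannabis | 0.200 | 0.333 | 1.67 | 39% |
| Alcohol | 0.300 | 0.462 | 1.54 | 47% |
| Both | 0.060 | 0.154 | 2.56 | 36% |
| Either | 0.440 | 0.641 | 1.46 | 65% |

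If every cannabis user also drinks, both equals cannabis (39%) and either equals alcohol (47%). The outcomes are different quantities, each with a valid relative risk. The composite has more power in the first case; in the second it equals alcohol alone.

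**Step 3: how often H1c would be called supported.** This was simulated with 200,000 replicates per setting. The test was an unadjusted Wald test on log RR, counted as support when z > 1.96 with DSP higher. The within-group correlation (phi) was 0.3, 0.5 or 0.7. Normal-phase use ran from 10% to 40%, or from 10% to 30% for any substance whose risk was doubled. Ranges are over feasible settings.

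| Truth | Any-use composite | One suffices | Both required |
|---|---|---|---|
| Neither differs | 0.9–1.8% | 0.7–3.4% | 0.01–0.5% |
| One differs, RR 2 | 5.6–72.9% | 25.8–92.2% | 0.2–1.8% |
| One differs, RR 1.5 | 3.1–38.8% | 6.5–57.7% | 0.1–1.8% |
| Both differ, RR 2 | 34.0–96.1% | 36.4–98.5% | 9.8–87.7% |
| Both differ, RR 1.5 | 10.1–63.4% | 10.4–77.2% | 1.0–44.7% |

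The first row counts only results with DSP higher. Counting either direction, two independent tests at 0.05 give 1 − 0.95² = 9.75% for at least one false positive, and three give 1 − 0.95³ = 14.3%.

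The *one differs* rows are errors only if *and* is a strict requirement that both substances differ. If H1c simply lists two outcomes, finding the one that differs is a correct result. In the *both differ* rows, requiring both loses power.

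**Step 4: which reading the text favours.** H1a, in the same Aim 1 sentence, also joins several outcomes with *and*, and the analysis section tests H1a and H1b outcome by outcome. Read the same way, H1c lists two outcomes. The abbreviation SU in the Aim 1 description is no evidence for a composite: the other labels in that sentence are also umbrella terms covering several measures.

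**The case for a change.** The best case for a change is that *and/or* does not define a binary outcome. The analysis sentence for H1a and H1b commits to testing each outcome, and the H1c sentence does not repeat this, so the parallel persuades without proving. The plan also foresees looking at substance-use distributions and running preliminary analyses, which leaves room to settle the outcome late. One or two sentences would close the gap, with no new data or visits.

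What stands is that the ambiguity is genuine and nothing in the document resolves it. A report of H1c should say which past-month outcome or outcomes were used and confine its conclusion to them: an any-use result speaks only to any use.

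What does not stand is the step from there to a defect in the analysis. The high percentages in the *one differs* rows depend on a strict *and* and on a decision rule that the plan never states. The wide ranges reflect assumed use rates and correlations. The effect-size argument fails because the measure is named and no clinical threshold is set.

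**Conclusion.** No change to the plan is called for. The odds wording is a clerical slip: the analysis sentence fixes relative risk, and the direction and null are the same for either measure. The open outcome definition is a gap that analysts can fill sensibly, most naturally with cannabis and alcohol as separate past-month yes/no outcomes, each with its own relative risk and interval. A composite is also defensible; it may gain power but cannot say which substance differs. Requiring both fits a literal *and* but costs power. That is a trade-off with no reading best throughout.

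As for size, the measure alters only how an effect is expressed (RR 2.00 against OR 2.25 to 3.50 at assumed normal-phase use of 10% to 30%). When neither substance differs, every reading calls H1c supported in under 5% of simulated studies, counting DSP-higher results only. The larger contrasts arise when one substance differs and *and* is read strictly. All these figures rest on assumed rates, effects, correlation and alpha, without covariate adjustment. H1c is an observational comparison; the randomised Aim 2 analysis is unaffected.

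### Aim 2 does not say how the T1 baseline enters the mixed model; the ordinary reading yields a difference in mean change, usually less precise than a baseline-adjusted estimate

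*Combined protocol and SAP*

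**What the plan says.** The Aim 2 paragraph of Statistical Considerations gives the model in one sentence: "Mixed effect models will be used to test the effect of group on changes in each" a priori outcome, with control for confounders judged relevant. It gives no equation, time term, interaction or covariance structure.

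The opening paragraph of the same section says that "all models will be adjusted for potential confounding factors (e.g., sex"; sex is the only example, and the T1 value of the outcome is not named. That paragraph also commits the experimental study to an intent-to-treat analysis of everyone randomised, and says "We will calculate actigraphy and EMA summary measures", which points to one summary per phase for those outcomes.

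Study Design & Methods defines two occasions. For T1: "The Laboratory protocol (aka T1 or Baseline phase) compares a group of DSP adolescents to a group of normal phase adolescents". For T2: "In the Experimental protocol (aka T2 or Post-Manipulation phase), we will probe whether stabilizing circadian phase in the DSP group" improves sleep and neurobehavioural function. The planned sample is "divided between 100 DSP and 50 normal phase teens", and only the DSP teens are eligible for the Experimental protocol.

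**The concern.** H2a and H2b are the trial's randomised hypotheses, and each covers several outcomes. The sentence fits at least three models: group-by-time with free baseline means, group-by-time with a common T1 mean, and an analysis with T1 as a covariate.

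The first is the ordinary reading. With two occasions and complete data it reduces to the difference in mean change. The named adjustment does not help there: sex entered as a main effect shifts T1 and T2 equally and cancels from the change.

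Two things are at stake. One is precision, in a comparison limited to at most 100 participants. The other is pre-specification: the candidate models can give different estimates on the same data, outcome by outcome, and the plan leaves the choice open.

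**Working it through.** **Inputs.** From the documents: two phases (T1, T2), a randomised comparison, and 100 DSP teens as the upper limit for Aim 2. Not in the documents, so assumed: 1:1 allocation (50 per arm), two-sided 5% level, effect of 0.5 T1 SD, complete data, r from 0.3 to 0.9, and a T2/T1 SD ratio k of 0.8, 1 or 1.2. The plan states no power or sample-size figure for Aim 2, so there is none to reproduce.

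**Formulas** (T1 SD = 1, T2 SD = k, variance per person):

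- Var(change) = 1 + k² − 2rk
- Var(adjusted) = k²(1 − r²)
- Difference = (1 − rk)², never negative and zero only when k = 1/r
- SE = √(2·Var/50); power = Φ(0.5/SE − 1.96); effect detectable with 80% power = 2.80 × SE

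**Equal variances (k = 1).** The ratio simplifies to (1 − r²)/[2(1 − r)] = (1 + r)/2. Paired entries are change / adjusted.

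| r | Variance ratio | SE | Power | Detectable effect (SD) | n per arm for 80% power |
|---|---|---|---|---|---|
| 0.3 | 0.91/1.40 = 0.65 | 0.237 / 0.191 | 56% / 75% | 0.66 / 0.53 | 88 / 58 |
| 0.5 | 0.75/1.00 = 0.75 | 0.200 / 0.173 | 71% / 82% | 0.56 / 0.49 | 63 / 48 |
| 0.7 | 0.51/0.60 = 0.85 | 0.155 / 0.143 | 90% / 94% | 0.43 / 0.40 | 38 / 33 |
| 0.9 | 0.19/0.20 = 0.95 | 0.089 / 0.087 | over 99% / over 99% | 0.25 / 0.24 | 13 / 12 |

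**Unequal variances** (adjusted/change variance ratio).

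| k | r = 0.3 | r = 0.5 | r = 0.7 | r = 0.9 |
|---|---|---|---|---|
| 1.2 | 1.310/1.72 = 0.76 | 1.08/1.24 = 0.87 | 0.734/0.76 = 0.97 | 0.274/0.28 = 0.98 |
| 0.8 | 0.582/1.16 = 0.50 | 0.48/0.84 = 0.57 | 0.326/0.52 = 0.63 | 0.122/0.20 = 0.61 |

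At k = 1.2 and r = 0.5, power is 61% for change and 67% for the adjusted estimate.

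**Simulation checks (k = 1, 50 per arm).**

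- t-tests over 8,000 runs gave power (change/adjusted) of 56/74%, 69/81% and 89/93% at r = 0.3, 0.5 and 0.7.
- A common-T1-mean model with unstructured covariance, over 1,500 runs per r, had empirical variance ratios of 0.64, 0.76, 0.82 and 0.95 against the free-baseline contrast at r = 0.3, 0.5, 0.7 and 0.9. Both means lay within 0.006 of the true 0.5, so neither estimator is biased.

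**The models on one simulated dataset** (r = 0.5, chance T1 arm difference −0.16).

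| Model | Estimate | SE |
|---|---|---|
| Free-baseline group-by-time (equals difference in mean change) | 0.538 | 0.198 |
| Same, with sex as a main effect | 0.538 | not computed |
| Same, with sex-by-time | 0.545 | not computed |
| Common T1 mean, unstructured covariance | 0.476 | 0.176 |
| ANCOVA on T1 | 0.476 | 0.179 |

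The sex main effect leaves the estimate where it was. Using T1 does change both the estimate and its SE.

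**The case against.** The strongest reply is that nothing here is an error. The difference in mean change is unbiased under randomisation, its inference is valid, and it matches hypotheses worded as advances, increases and reductions. The wording does not exclude a constrained-baseline model, and the covariate list is open, so the loss belongs to one reading of the plan. Every input to the power figures is assumed, and the variance ratio runs from 0.50 to 0.98 over the range shown. In the worked dataset the conclusion would not change: z is 0.538/0.198 = 2.72, 0.476/0.176 = 2.70 and 0.476/0.179 = 2.66.

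Most of this is fair. This is a matter of efficiency and specification, not validity, and the power table is illustrative. But permitting a model is not specifying it. A baseline value in a randomised comparison is a prognostic covariate rather than a confounder, so an instruction to control for confounders does not clearly bring it in. One dataset with similar z values says nothing against the average gain; it does show estimates of 0.538 and 0.476 from the same data. Hypotheses about change are also answered by the baseline-adjusted contrast: with a common T1 mean, the arm difference at T2 is the arm difference in change.

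Three practical limits also stand. With missing T2 values, the mixed-model estimate no longer equals the raw difference in mean change exactly. The structure of the task and fMRI data is not stated, so one value per phase is an assumption for those outcomes. Naming the baseline model does not close the choice of other covariates.

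**Conclusion.** The concern holds. The role of T1 in the Aim 2 model is unspecified, and the ordinary free-baseline reading gives the difference in mean change. In large samples that estimate is never more precise than the baseline-adjusted one; in small samples adjustment costs about one degree of freedom.

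The gain from adjustment is substantial if r is 0.3 to 0.5 with similar variances (11 to 19 percentage points of power under the assumptions above). With equal variances it is small at r = 0.7 and negligible at 0.9, and it is nil when the T2/T1 SD ratio equals 1/r. Where this trial falls cannot be told from the documents. No bias is alleged. The change is worth making because it costs almost nothing and settles the model for every H2 outcome.

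**What to change.** Replace the Aim 2 sentence with wording such as:

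> For each a priori outcome, the T1 and T2 values of the randomised DSP participants are modelled jointly, with a common T1 mean for the manipulation and control arms and an unstructured covariance. The arm difference at T2 is the estimate. Covariates enter with their interaction with time. All randomised subjects with any T1 or T2 value are included.

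The unstructured covariance matters: a random intercept alone would force equal T1 and T2 variances. A close alternative is ANCOVA of T2 on arm, T1 and the covariates, with multiple imputation for missing T2; it also needs a stated rule for missing T1. In either form, list the covariates by name, and say that the same model applies on the transformed scale where a transformation is used.

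The cost is SAP wording only. T1 and T2 are already collected, and randomisation justifies the common T1 mean. The wording should be fixed before Aim 2 is analysed. The documents do not say whether that has happened; if it has, report the baseline-adjusted analysis beside the original and label it as added later.
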